5.6. Randomization, blinding and stratification

Randomization: Randomization will use an arm equivalence design to promote equal numbers of participants for each order schema. Randomization will occur within 72 hours of completion of the screening and baseline assessments collected at the screening visit and 72 hours prior to study intervention initiation. The order in which the doses are administered will be randomized so that some data will be available for both doses in case of dropouts after the first visit.

Blinding: All participants will be blinded to the dose they will be receiving at each visit. We have developed a formulation that tastes and looks very similar at each dose. The investigator administering the intervention and the analyst performing the LC-MS analysis of collected plasma will be blinded as to the dose of the product administered. The LC-MS analyst will also be blinded as to the time point of collection. The principal investigator, [name], is authorized to break the blind.

Stratification: Participants will be stratified by gender so that each dose level (2g or 4g) is administered to equal numbers (n=8) of each gender. Although exploratory in nature, contrasts between gender and cognitive impairment status will be calculated for powering and pilot data purposes.

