10.6. Specimen analysis

Each CAP derived analyte will be identified by its retention time and characteristic mass spectral fragmentation pattern using selected reaction monitoring. The peak area ratio to the appropriate internal standard will be identified and evaluated against the standard calibration curve of each analyte. Each analyte's concentration will be used to generate a concentration-time curve for pharmacokinetic profiling. Pharmacokinetic (PK) profiling of the triterpenes, CQAs and their metabolites will use non-compartmental analysis (NCA) to calculate common PK parameters such as peak concentration (C_{max}), the time at peak concentration (t_{max}) and the total 10 hour bioavailability represented by the total area under the curve (AUC_{0-10}). These will be compared to the mouse data in order to assess appropriateness of dosing level. Other calculable NCA metrics will also be determined, such as the elimination half-life ($t_{1/2}$) calculated from the profile tails and the mean residency time (MRT) of the compounds in plasma. Descriptive assessment will be done at each of the doses to give basic PK summarization of the various CA compounds and total antioxidant compounds measured by FRAP. NRF2 antioxidant pathway related gene and/or protein levels will be compared in PBMCs from the screening visit, the baseline study visit sample and hourly up to 6h following CAP administration. Dose dependence of the study outcomes will be determined by evaluation of the within-subject differences in study outcomes between the 2g and 4g CAP doses.

Assumptions of normality will be confirmed using outcome density distributions alongside utility from formal tests, such as the Anderson-Shapiro. In instances of normality violation, statistical transformation such as natural logs and square roots will be considered as will non-parametric equivalent tests such as the paired Wilcoxon rank-sum test. Standard diagnostics will be very conservative given the limited number of available subjects but clearly obvious outliers will be removed as necessary. Non-continuous variables such as t_{max} will have frequency distributions compared between doses using chi-square testing. Although all CA compounds of interest and PK parameters are defined a priori, multiple comparison correction to p-values will be applied as necessary, with final two-tail significance defined at $p < 0.05$.

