10.8. Sample size

Sample size was calculated based on the primary outcome measures of C_{max} and AUC. Changes in the response values from the literature were taken from Grimaldi et. al.⁴⁵ for two outcomes, peak concentration (C_{max}) and bioavailability/area-under-the-curve (AUC), at two treatment doses. With respect to C_{max} , estimations from G*Power indicated a sample size of 6 would be sufficient to detect the established criterion difference (critical $t=2.57$).

The post-treatment mean difference in C_{max} from the literature was found to be 0.66 and was replicated during simulation with confidence intervals indicating a significant difference {0.36, 0.96}. Both the observed mean and median test statistics was found to be greater than the critical t (mean $t=4.23$, median $t=3.88$). Mean power was found to be slightly lower than expected (84% versus 86%) although median power was significantly larger (92%). Accordingly, six subjects would be sufficient to detect a difference in C_{max} between two doses of CAP. With the enrollment of 8 subjects, the study will be sufficiently powered even with a dropout rate of 25%.

Similar results were found for bioavailability, as measured as AUC, although at an attenuated effect, with an indicated increase in subject count to a minimum of 7 (critical $t=2.45$). Simulation verified a mean difference of 5.25 that would be expected to be significant based on the simulated confidence intervals {2.43, 8.09}. AUC was also found to be similarly powered, with a mean observed power of 83% and a median power of 93%. Accordingly, a sample size of seven is more than sufficient to meet the proposed criterion for CAP analyte bioavailability. With the enrolment of 8 subjects, the study will be sufficiently powered with 1 dropout (14%). Given the short duration of the study, we expect that a dropout rate of only 1 subject is reasonable. Eight total subjects were proposed for the dose comparison of Aim 1, which would allow for reductions in the detectable shifts of both peak concentration (37% of literature effect; $\Delta C_{max}=0.42$) and bioavailability (31% of literature effect; $\Delta AUC=3.63$) allowing for even greater powering to detect a dose effect of CAP.

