Based on previously described bench results, gender is anticipated to potentially play a role in CAP metabolism, which may limit the ability to pool results. Maintaining the variances used in the calculations detailed above, the study would still be powered to see the anticipated dose effects within either gender with reduced powers of 75% and 67% for C_{max} and AUC bioavailability respectively.

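### Section 10.6 gives no model for gender-specific dose effects, and the 75% and 67% within-gender power in 10.8 is about 54% and 45% under the plan's own two-tailed rule

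*Combined protocol and SAP*

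**What the plan says.** Section 4.3.1 and the synopsis (Sample size and population) set 4 women and 4 men. Section 2.1 promises to evaluate gender differences in bioavailability and pharmacokinetics. On randomisation the document contradicts itself. Section 5.6 says "Participants will be stratified by gender so that each dose level (2g or 4g) is administered to equal numbers" of each gender, while the synopsis says the randomisation is not stratified. Section 5.6 also announces exploratory gender contrasts, without a model.

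Section 10.6 states that dose dependence "will be determined by evaluation of the within-subject differences in study outcomes between the 2g and 4g CAP doses", "with final two-tail significance defined at" p < 0.05. It offers transformation or a paired Wilcoxon test if normality fails. It names no gender term.

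Section 10.8 finds that for Cmax "a sample size of 6 would be sufficient to detect the established criterion difference", with critical t 2.57 and mean power 84%. For AUC it gives n=7, critical t 2.45 and mean power 83%. It then says that "gender is anticipated to potentially play a role in CAP metabolism, which may limit the ability to pool results" and, keeping the same variances, quotes 75% and 67% power within a single gender.

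**The concern.** The plan raises the possibility that men and women cannot be pooled and quotes a power for that case, but does not say what would then be fitted or what would trigger it. The choice between pooling and splitting would be made after the data are seen, for both primary parameters. If the reader takes the quoted power as reassurance, a null result in one gender would be over-read, because the chance of missing the planned effect is nearer one half than one quarter or one third.

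A gender difference in overall exposure cancels in the within-person difference. Only a dose effect that differs by gender matters here.

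**Working it through.** **Inputs.** Section 10.8: mean power 84% at n=6 (Cmax) and 83% at n=7 (AUC); critical t 2.57 and 2.45; common variance across genders. Section 10.6: two-tailed 5%. Section 4.3.1: 4 per gender. The SD of the differences is not given, so the standardised difference δ (mean difference divided by the SD of the differences) is back-solved.

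**Formula.** For a paired t-test on n differences, power = P(|T| > t crit), where T is noncentral t with df = n − 1 and noncentrality δ√n.

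**1. Sidedness.** The two-sided 5% critical values are 2.571 for df 5 and 2.447 for df 6. They match the plan's 2.57 and 2.45, so its main calculation is two-sided.

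**2. Effect size.** 84% at n=6 gives δ = 1.516; 83% at n=7 gives δ = 1.325.

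**3. Reproducing 75% and 67%.** With n=4, noncentrality is 2δ and df is 3 (critical t 3.182 two-sided, 2.353 one-sided).

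| Source of δ | δ | Two-sided, n=4 | One-sided, n=4 |
|---|---|---|---|
| Cmax, mean power 84% | 1.516 | 54.1% | 74.3% |
| Cmax, expected power 86% | 1.562 | 56.3% | 76.3% |
| AUC, mean power 83% | 1.325 | 44.5% | 64.7% |
| AUC, interval 2.43 to 8.09 | 1.374 | 47.0% | 67.3% |

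In the last row the SD is (2.83/1.96) × √7 = 3.82, and 5.25/3.82 = 1.374. The plan's figures appear only in the one-sided column.

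Other readings of 10.8 give higher two-sided values. The median powers (92%, 93%) give 64.6% and 56.7%. Treating the Cmax interval as a t-interval gives δ = 2.31 and 85% at n=4, but that δ implies 99% power at n=6, which conflicts with the plan's 84% to 86%.

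**4. One model on all 8.** Write D = β0 + β1·g + error, with D the 4 g minus 2 g difference and g = +1 or −1 for gender. The dose effect in a gender is β0 ± β1, with variance σ²/8 + σ²/8 = σ²/4. That equals the variance of a mean of 4, so the noncentrality stays at 2δ. The error is now estimated on 8 − 2 = 6 df (critical t 2.447).

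| Within-gender power, two-sided | Cmax | AUC |
|---|---|---|
| Separate tests of 4 (df 3) | 54.1% | 44.5% |
| One model (df 6) | 71.6% | 60.2% |
| One model with a period term (df 5) | 68.1% | 56.9% |

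The gain from one model is 17.5 and 15.7 points, or about 14 and 12 with a period term. The last row assumes the two dose orders are balanced within each gender.

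**5. Cost to the overall dose test.** At n=8 the noncentrality is δ√8 = 4.288 and 3.748. Without the term (df 7), power is 95.5% and 89.3%. With it (df 6), and no gender difference in dose effect, it is 94.3% and 87.5%, a loss of 1.2 and 1.8 points.

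**6. Sensitivity (simulation; the ratios are assumptions, since the plan gives none).**
- SDs in ratio 3:1 between genders: the common-variance within-gender test has type I error of about 14% in the more variable gender and 0.4% in the other. Separate tests hold 5%.
- Dose effects in ratio 3:1 with equal SDs: one-model power in the gender with the smaller effect is only about 25% (Cmax) and 20% (AUC).
- Dose effects and SDs both in ratio 2:1: overall power without and with the term is 94.7% and 93.6% (Cmax), 88.2% and 86.9% (AUC).

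**The case against.** The strongest reply is that this is an eight-person pilot whose gender contrasts are declared exploratory, and that 10.8 contains only a remark about power. It names no separate test, and 5.6 leaves room for a joint model. That stands: two tests of 4 are the natural reading, not a written procedure. It does not rescue the quoted power, and leaving the procedure open is the reason to specify it.

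A second reply is that the common-variance model is least safe where it is most wanted. If exposure is proportional to dose and one gender has higher exposure, the raw-scale SD would plausibly rise with the effect, and the within-gender type I error is then distorted as in step 6. This also stands. It is why the log scale is preferable: proportional kinetics then give both genders the same dose ratio and similar variance. Section 10.6 allows logs, but only if normality fails.

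A reader might also infer that leaving out gender weakens or biases the overall dose comparison. With 4 and 4, the average dose effect is not biased. The term can raise overall power when dose effects differ and SDs are equal, but that rests on ratios absent from the plan, and at 2:1 the gain disappears once SDs scale with the effects.

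**Conclusion.** The point holds for the gender-specific analysis. Section 10.6 has no model for it, and the within-gender power in 10.8 is overstated by about 21 points for Cmax (75% against 54%) and 22 for AUC (67% against 45%) on the plan's mean powers and two-tailed rule. A joint model recovers 16 to 18 points but still falls short of 80%.

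These figures assume normal differences, the back-solved δ, common variance and the same dose effect in each gender. They are on the raw scale; the documents give no inputs for log-scale power.

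The documents do not support three stronger readings: that gender is settled as a stratification factor (the synopsis denies it), that the plan asserts a gender effect on metabolism (10.8 says only that one is possible), or that the overall dose test needs the gender term. For that test the term is a trade-off.

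**What to change.** In 10.6, state that for Cmax and AUC0-10 the dose effect in each gender, and the difference between genders, come from one model of the within-subject 4 g minus 2 g differences with sum-coded gender, fitted to all 8 people and preferably on the log scale. Say whether a period term is included, and require the variances to be compared between genders, recognising that 4 per group gives a weak check.

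In 10.8, replace 75% and 67% with about 72% and 60% (common variance, equal dose effects), about 68% and 57% if a period term is fitted, or about 54% and 45% if the genders are tested separately. Remove the statement that the study remains powered within each gender.

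Reconcile the synopsis with 5.6 on stratification, and correct or explain the n=8 in 5.6, since there are only 4 of each gender.

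The cost is wording only, with no extra participants, visits or samples. Statistically it is one error df, about 1 to 2 points of overall power if the dose effect does not differ by gender, plus reliance on equal variances, which 10.8 already assumes.

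### The within-gender powers of 75% (Cmax) and 67% (AUC) do not follow from the plan's two-sided paired calculation; separate tests on 4 people per gender give about 55% and 45%

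*Combined protocol and SAP*

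**What the plan says.** Section 10.8 sizes the study on two primary measures.

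- **Cmax:** 6 people, critical t 2.57. The expected power is 86%; simulation gave a mean power of 84% and a median of 92%. The simulated test statistics were mean t 4.23 and median t 3.88. The difference is 0.66, with interval 0.36 to 0.96.
- **AUC:** "with an indicated increase in subject count to a minimum of 7", critical t 2.45, "with a mean observed power of 83% and a median power of 93" per cent. The difference is 5.25, with interval 2.43 to 8.09.

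The section then says gender may affect metabolism, "which may limit the ability to pool results". It describes its approach to that case as "Maintaining the variances used in the calculations detailed above". Its conclusion is that the trial "would still be powered to see the anticipated dose effects within either gender with reduced powers of 75% and 67" per cent.

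Elsewhere:

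- Section 10.6 bases the dose comparison on within-subject differences and sets two-tailed significance at 0.05.
- The synopsis gives 4 male and 4 female participants.
- Section 5.6 calls the gender contrasts exploratory, for powering and pilot data.
- Section 4.3.1 says the study remains powered with six completers and names no endpoint.

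**The concern.** If the variances and the test are kept and only the number of people falls to 4, the power is fixed by what 10.8 already reports. With 3 degrees of freedom the two-sided critical value rises to 3.18, so a larger fall than from 84% to 75%, or from 83% to 67%, would be expected.

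The sentence covers the situation in which the genders cannot be pooled. A reader would take from it that each gender can stand alone. If the true power is near one half, a non-significant result in one gender says very little. Section 5.6 wants these contrasts for powering later work, so the printed power should be right. Section 4.3.1 raises a related problem for a primary endpoint: it treats six completers as enough without excepting AUC.

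**Working it through.** **Method.** For n people and standardised within-subject difference dz (mean difference divided by the SD of differences), the paired t statistic is noncentral t with n − 1 df and noncentrality dz·√n. Two-sided power is P(|T| > t(0.975, n − 1)). The SD is not printed, so dz is solved from each stated power and then used at n = 4.

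**Checking the plan's test.** t(0.975, 5) = 2.571 and t(0.975, 6) = 2.447. These match the printed 2.57 and 2.45, so the sizing is a two-sided paired test at 0.05. For 4 people, t(0.975, 3) = 3.182.

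**Power at n = 4.** The noncentrality is dz·√4 = 2·dz.

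| Endpoint and stated power | dz | 2·dz | Two-sided, df 3 | One-sided 5%, df 3 | Two-sided, pooled variance, df 6 |
|---|---|---|---|---|---|
| Cmax, 84% at n = 6 (mean) | 1.516 | 3.03 | 54.1% | 74.3% | 71.6% |
| Cmax, 86% at n = 6 (expected) | 1.562 | 3.12 | 56.3% | 76.3% | 74.1% |
| Cmax, 92% at n = 6 (median) | 1.737 | 3.47 | 64.6% | 83.3% | 82.3% |
| AUC, 83% at n = 7 (mean) | 1.325 | 2.65 | 44.5% | 64.7% | 60.2% |
| AUC, 93% at n = 7 (median) | 1.570 | 3.14 | 56.7% | 76.7% | 74.5% |

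The plan states 75% and 67%. No two-sided df 3 entry reaches either.

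**Working backwards.** A two-sided 75% at n = 4 needs dz = 1.987, which would be 96.9% power at n = 6. A two-sided 67% needs dz = 1.791, which would be 97.4% at n = 7. Section 10.8 reports 84–92% and 83–93%.

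**Cross-check on the simulated t values (Cmax, n = 6).** The mean of a noncentral t on 5 df is 1.189 times its noncentrality.

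- Mean t: 4.23/1.189 = 3.556, and dz = 3.556/√6 = 1.452. That gives 81% at n = 6 and 51% at n = 4.
- Median t: 3.88 corresponds to noncentrality 3.649 and dz = 1.490. That gives 83% at n = 6 and 53% at n = 4.
- Without the bias correction, the same statistics give 64% and 57% at n = 4.

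**Cross-check on the intervals.**

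- AUC half-width (8.09 − 2.43)/2 = 2.83. Read with 1.96, SD = 2.83·√7/1.96 = 3.82 and dz = 5.25/3.82 = 1.374. That is 85.5% at n = 7, consistent with the stated range. At n = 4 it gives 47.0% two-sided, 67.3% one-sided and 63.3% with pooled variance.
- Cmax half-width 0.30. Read with 1.96, dz = 1.760: 92.6% at n = 6 and 65.6% two-sided at n = 4.
- Read as t-intervals, dz is 2.309 (Cmax) and 1.716 (AUC). At n = 4 that gives 85% and 64%, but it implies 99% at n = 6 and 96% at n = 7, which contradicts the stated powers.

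**Dropouts.**

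- If one person leaves, that gender has 3. A separate two-sided test then has 32–34% (Cmax) and 27% (AUC) on the mean or expected powers.
- AUC with six completers overall has 73.8% on the mean power and 86.3% on the median power.
- All 8 pooled have about 96% (Cmax, dz 1.516–1.562) and 89% (AUC, dz 1.325).
- One dropout of eight is 1/8 = 12.5%. The printed 14% is 1/7.

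**The case against.** **A two-sided route to the stated pair.** Section 10.8 also gives detectable shifts with 8 people: 0.42 for Cmax and 3.63 for AUC. If these are taken at 85% two-sided power, dz for the shift is 1.238. The full effects are then 1.238 × 0.66/0.42 = 1.946 and 1.238 × 5.25/3.63 = 1.791, and n = 4 gives 73% and 67%; at 86% power it gives 75% and 68%. However, the plan states no power for these shifts, and this route implies about 96–98% at n = 6 and n = 7, against the reported 84% and 83%. Taken as one-sided at 80% power, the same shifts give dz 1.54 and 1.41. Those yield 75% and 69% one-sided at n = 4 and 85% two-sided at n = 6, which fits the rest of the section better.

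**Mean power may be averaged observed power.** If so, it understates true power. A Cmax dz near 1.65 would fit both the mean and the median, and an AUC dz of about 1.45–1.5 would do the same. At n = 4 these give about 61% and 51–53%, still short of 75% and 67%. The expected 86% and the mean t of 4.23 also point lower.

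**Pooled variance.** A contrast using a variance pooled over both genders (df 6) comes near 75% for Cmax on the mean or expected powers, but gives only 60–63% for AUC on the mean power or the interval read with 1.96. On the median powers it overshoots both. The plan describes no such model.

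**What stands.** The one-sided explanation is an inference. The exact replacement values depend on an SD that is not printed. The gender contrasts are already labelled exploratory in 5.6, and the primary comparison does not depend on this sentence. Section 10.8 does give the AUC minimum correctly, so 4.3.1 is incomplete rather than the only statement on the matter.

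**Conclusion.** The concern holds. Under the test that 10.8 and 10.6 define, separate analyses of 4 people per gender have about 54–56% power for Cmax and 45% for AUC on the mean or expected powers, or 65% and 57% on the median powers. The stated 75% and 67% are about 20 points too high on the former basis and about 10 on the latter. Saying the study remains powered within either gender is not supported.

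This rests on four assumptions: dz is back-solved from the stated powers; effect and variance are the same in each gender; differences are normal; and each gender is tested separately. It is not an upper limit, since a pooled-variance model would do better.

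The consequence is limited. The contrasts are exploratory and the pooled comparison of 8 people keeps about 96% and 89%. Separately, 4.3.1 and 10.8 disagree on whether six completers suffice for AUC, which is also primary.

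**What to change.** - **Section 10.8, within-gender sentence.** State the test, n, df, sidedness and SD of differences. Restate the powers two-sided: about 55% (Cmax) and 45% (AUC) for separate tests on 4 people, to be replaced by exact values from the sponsor's actual SD. If a pooled-variance contrast is intended, describe the model and give its figures. Remove the claim that the study remains powered within either gender, and add the exploratory label from 5.6.
- **Section 4.3.1.** Limit the six-completer statement to Cmax. Say that AUC needs 7, with about 74% power at six on the stated mean power.
- **Minor.** Correct 14% to 12.5% in 4.3.1 and 10.8. Make the synopsis (no stratification) and 5.6 (stratified by gender) agree, and reconcile the n=8 of each gender in 5.6 with the 4 and 4 in the synopsis.

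The cost is a few sentences. No participants are added and the primary analysis does not change; the only downside is that the stated figures look less favourable.

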10.9. Data quality and management

The principal investigator will oversee the management of the participants, intervention, and analysis, which will be carried out by the clinical investigators, research statistician, and research assistant. Data entry, quality control and preparation, and participant management will be ongoing throughout the study.

The principal investigator will oversee study progress including recruitment, retention, demographics, study participant status and error rates pertaining to inclusion/exclusion criteria and the study protocol. Tabulation of study data will have both physical and digital formats available. A member of the study team will record data from each study visit and phone visit on paper case report forms. Physical copies of the case report forms will be scanned into the participant's REDCap encounter, kept in participant-specific binders and kept available for comparison against the final study database. Digital documentation will use the REDCap

database system, which will maintain quality of integrity using prescribed logic rules inherent to the system. Data will be input immediately upon the participant's visit and double-checked within 48 hours for accuracy by a separate member of the study team or the Principal Investigator. This will include limited options for responses, protection against redundancy and double-data entry, and locking of the database for information entry upon study completion. This combination of steps will promote cohesiveness of study outcomes from study visit to data entry while maintaining the necessary protection of participant privacy. All plasma concentration calculations will be performed using a Microsoft Office Excel database by study personnel and double-checked within one week by a second member of the study team to ensure accuracy. The computer files will be protected with a password and only appropriate study personnel will have access to the database.

